4.5 Study Rationale

As outlined in the Clinical Summary (Section 4.4.2), BoNT/A-DP should be a valuable option for the treatment of glabellar lines and other indications. BoNT/A-DP

has been shown to be safe and well tolerated when administered at doses up to 360 U, which is well above the 20 U dose planned for use in this study. The current Phase 3 study is designed as a randomized double blind study to assess the efficacy and safety of BoNT/A-DP in the treatment of glabellar lines in comparison with placebo, followed by an open label extension study to evaluate efficacy after repeat treatments and long term safety. Data obtained from this study will provide evidence of efficacy and subject safety in a controlled clinical trial and will be used for registration purposes. The dose rationale for this study is described in Section 4.5.1.3.

4.5.1.1 Study Design Justification

This will be a multicenter, double blind, placebo-controlled study, followed by an open label extension. The study will take place in Europe and the US.

To allow all subjects to profit from treatment and to obtain adequate safety data for BoNT/A-DP treatment, the study will be comprised of two parts. The first part will comprise a double blinded treatment cycle comparing BoNT/A-DP with placebo (ratio 3: 1 respectively) and will be used for the determination of primary and key secondary efficacy endpoints. The 3:1 ratio was selected to increase the number of subjects on active IMP, thus extending the safety database and still providing a sufficient number of placebo subjects for relevant comparisons in efficacy and safety. The second part of the study will be an open label safety extension, in which all subjects (regardless of initial treatment group assignment) will receive BoNT/A-DP, to assess long term safety of the treatment and efficacy after repeat treatments.

A total of 700 subjects will be enrolled, which should allow for a precise estimate of response rate and for post-hoc sensitivity analyses.

4.5.1.2 Justification for Schedule

The study schedule includes a maximum of four permitted treatments per subject (four treatment cycles), separated by a minimum interval of 12 weeks, during the study time frame of up to 60 weeks in treatment phase. A minimum interval of 12 weeks between treatments was selected, since the median duration of effect has been reported to be 85 days (12.1 weeks)³¹ and this treatment interval has been evaluated in several repeat treatment studies^{32,33}.

However, since treatment duration of 120 days³⁴, 17.1 ± 6.5 weeks³⁵ or four to six months³⁶ have been reported and re-treatment intervals have been estimated at a mean of 3.9 months³⁶, the schedule has been devised flexibly such that subjects can obtain re-treatment when they qualify (according to the "Eligibility Criteria for Re-

treatment" Section 7.3), which can be at week 12 at the earliest or at four weekly intervals thereafter. Hence, the duration of effect of BoNT/-DP will be evaluated in the first treatment cycle compared with placebo. The duration of effect of BoNT/-DP after repeat treatment will be assessed in the open label extension study. The duration of effect has been reported to increase with repeat treatment³⁷.

4.5.1.3 Dose Justification

The dose selected is 20 U, where 1U is defined as "the calculated median intraperitoneal lethal dose (LD₅₀) in mice". Study HG-11-01 performed in South Korea demonstrated that a dose of 20 U BoNT/A-DP per treatment was safe and highly efficacious in the treatment of glabellar lines, with reported responder rates similar to those of the [REDACTED] comparator product administered at the same dose (20 U). The potency units of botulinum toxins for injection are specific to the preparation and assay methods utilized and are not interchangeable with other preparations³⁸ (historical data with similar products have confirmed the efficacy of a 20 U dose and current safety recommendations favour the use of such small doses³⁹; FDA Guidance for Upper Facial Lines).

4.6 Evaluation of Anticipated Risks and Benefits of the Investigational Medicinal Product to Human Subjects

4.6.1 Possible Benefits for the Subject

The benefit of participation in this study is the expected reduction in the severity of glabellar frown lines after treatment with BoNT/A-DP. Since the subjects recruited are also negatively impacted psychologically by their glabellar lines, it is anticipated that treated subjects will benefit in terms of quality of life (emotional and social functioning; improved self-perception). Subjects receiving placebo for the first treatment cycle will benefit from free medical screenings and follow-up provided to all study subjects and will benefit from treatment when they enter the open label study.

4.6.2 Possible Risks/Inconveniences for the Subject

Botulinum toxin drug products present a unique set of safety concerns related to the potential for local and distant spread of toxin effect. Therefore, an active evaluation of subjects for signs and symptoms of local and distant spread of toxin effect will be performed throughout the study at each study visit. Subjects will be warned about signs of the spread of toxin effects including asthenia, generalized muscle weakness, diplopia, ptosis, dysphagia, dysphonia, dysarthria, urinary incontinence, breathing difficulties and possible adverse events of special interest (AESIs, please see

Section 11.1). Respiratory, speech or swallowing difficulties can also result, which could be life threatening, however no definitive SAE reports of distant spread of toxin effect associated with cosmetic or dermatologic use of botulinum toxin at the labeled dose of 20 U (for glabellar lines) or 100 U (for severe primary axillary hyperhidrosis) have been reported to date. Baseline physical examinations will also be conducted to rule out pre-existing neurological or muscular deficiencies. In addition, key safety measures such as vital signs and pregnancy tests (where appropriate) will be conducted at suitable intervals to ensure no participating subjects are pregnant.

As is the case with all injected products, injection site reactions such as pain, tenderness, redness, induration and/or swelling may occur after administration. In addition, a number of other symptoms have been experienced by single subjects including pruritus, hypertonia, ptosis, headache, diplopia, edema and blurred vision. The most frequently observed injection site reactions were injection site pain and swelling. The vast majority of AEs were rated as mild.

In addition, as with any IMP, there may be unforeseeable risks associated with the use of BoNT/A-DP or placebo control. As a side effect of drawing blood, pain, hematoma, and in very rare cases an infection at the venipuncture site may occur.

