TC = telephone contact: including assessment of concomitant medication, AEs and AESIs¹⁵ (as per AESI manual) on weeks 2 and 8 of each open-label cycle (visits 9, 11, 14, 16, 19 and 21). If an AESI is reported during a telephone contact, subjects will be asked to come to the site for further assessment including a targeted physical examination as soon as possible) * Visit numbers correspond with specific treatment and assessments. If subjects are not eligible for re-treatment at the "Evaluation for Re-treatment" visit, they will return at 4 weekly intervals thereafter, until they are eligible for treatment. The subsequent visit number for the cycle will remain the same, but will be amended with "a, b, c" etc., corresponding to the time extended (at 4 weekly intervals) in that treatment cycle. For example, the first evaluation for re-treatment is at visit 7, week 12, however for subjects who are not eligible at week 12, but at week 16, this visit will be denoted "visit 7a", while "visit 7b" will denote week 20 in the first cycle and "visit 7c" will denote week 24 etc., with each additional letter corresponding to a time point 4 weeks later in that cycle.

** Time differences are measured from the previous treatment administered. A time deviation of ± 2 days is allowed for each visit, except for the week 1 visit in the first treatment cycle where a time deviation of ± 1 day is permitted. Sites must adhere to the schedule of events and visit windows and subjects must ensure they are available for those visits. However, if for practical reasons e.g. public holidays, a visit window cannot be met, a visit can be scheduled as close as possible to that visit window. However, any deviation from the visit schedule and its associated time windows will still be documented as a protocol deviation.

*** Full physical examination will include neurological assessment (including extraocular movements and cranial nerves) as well as assessment for muscle weakness. In addition, if the subject reports any symptoms related to Adverse Events of Special Interest (as detailed in the AESI Manual) a focused physical examination, to evaluate these symptoms will also be undertaken.

§ The ECG performed at screening is the baseline ECG. Laboratory and Anti-drug-antibody (ADA) test samples from screening are considered baseline values.

- 1 Depending on the duration of treatment effect, a maximum of 4 treatments is permitted.

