11.2 Adverse Events of Special Interest

A specific concern in treatment with botulinum toxin products is the potential for local and distant spread of toxin effect, a unique set of safety concerns related to use of botulinum toxin drug products (draft guidance for industry *Upper Facial Lines: Developing Botulinum Toxin Drug Products*). Therefore, subjects will be instructed and educated on possible warning signs and precautions and on rare AESIs through the Subject Information Sheet (SIS). Safety data related to this specific potential effect should be obtained through directed query at each study visit and if an AESI as below is reported a targeted physical examination should be conducted to evaluate for signs and symptoms of local and distant spread of toxin effect. Adverse events of special interest potentially suggestive of distant spread of toxin, include:

accommodation disorder	dyspnea	paresis
areflexia	extraocular muscle paresis	peripheral nerve palsy
aspiration	eyelid function disorder	peripheral paralysis
blurred vision	eyelid ptosis	pelvic floor muscle weakness
botulism	facial palsy	pneumonia aspiration
bradycardia	facial paresis	pupillary reflex impaired
bulbar palsy	fourth cranial nerve paresis	quadriparesis
constipation	hemiparesis	respiratory arrest
cranial nerve palsies	hypoglossal nerve paresis	respiratory depression
cranial nerve paresis	hyporeflexia	respiratory failure
cranial nerve paralysis	hypotonia	speech disorder
diaphragmatic paralysis	monoparesis	third cranial nerve paresis
diplopia	muscular weakness	trigeminal nerve paresis
dry mouth	paralysis	urinary retention
dysarthria	paralysis flaccid	vocal cord paralysis
dysphagia	paralytic ileus	vocal cord paresis
dysphonia	paraparesis	

The first AESI questioning will be undertaken (in accordance with the AESI Manual) prior to the first injection, in order to obtain a full baseline status of any concomitant diseases. If an AESI is reported, a targeted physical examination must be conducted. If reported during a telephone contact, subjects must come to the site for further assessment as soon as possible.

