11.6.1 Reporting Serious Adverse Events and Adverse Events of Special Interest

All SAEs and AESIs for all subjects occurring from the time of informed consent until the End of Study visit must be reported to CROMA Pharma GmbH or their representative **within 24 hours** of the knowledge of the occurrence. If considered at least possibly related to study treatment, SAEs observed after the End of Study visit must also be reported.

Paper SAE/AESI forms should be completed at the site and faxed to the relevant Medical & Safety Services Department [REDACTED] **within 24 hrs** of awareness of the event.

Fax number for SAE/AESI and Pregnancy reporting:

Email all sites:

[REDACTED]

For European sites

[REDACTED]

For North American sites

████████████████████

If the report is sent via email then the completed and signed SAE/AESI or Pregnancy report form must be attached to the email. A notification email of the event describing it in the email text is not sufficient.

There may be situations when an SAE/AESI has occurred and the investigator has minimal information to include in the initial SAE/AESI report to CROMA Pharma GmbH, or their representative. However, it is very important that the investigator always makes an assessment of causality for every event prior to transmission of the SAE/AESI report form. Minimum criteria are identifiable subject (number), a suspect product (i.e. IMP or concomitant medication), an identifiable reporting source (investigator/study-site identification) and an event or outcome that can be identified as serious or as an AESI. The investigator may change his/her opinion of causality in the light of follow-up information, amending the SAE/AESI report form accordingly. The causality assessment is one of the criteria used when determining regulatory reporting requirements for SAEs.

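### Urinary incontinence and asthenia are among the nine toxin-spread signs subjects are warned about but have no counterpart in the AESI list, so non-serious cases may miss AESI reporting and the AESI tables

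*Protocol*

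**What the plan says.** Protocol 4.6.2 commits the trial to active evaluation for local and distant spread of toxin effect at every study visit. It lists the signs that subjects will be warned about: "asthenia, generalized muscle weakness, diplopia, ptosis, dysphagia, dysphonia, dysarthria, urinary incontinence, breathing difficulties".

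Protocol 11.2 gives the AESI terms under the lead-in "Adverse events of special interest potentially suggestive of distant spread of toxin, include" and sets the examination trigger: "if an AESI as below is reported a targeted physical examination should be conducted". The terms closest to the two signs at issue are "muscular weakness", "urinary retention" and "pelvic floor muscle weakness".

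The footnote on physical examination in protocol 2.1, repeated in SAP Table 1, is worded more broadly: "if the subject reports any symptoms related to Adverse Events of Special Interest (as detailed in the AESI Manual) a focused physical examination".

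Protocol 11.6.1 sets the 24-hour reporting duty: "All SAEs and AESIs for all subjects occurring from the time of informed consent until the End of Study visit must be reported". Protocol 9.3.1 and the telephone-visit footnote to Table 9-1 require an unscheduled visit when an AESI is reported by telephone. Protocol 12.4.2 and SAP 8.7.2 tabulate AESIs separately from treatment-emergent adverse events (TEAEs). The SAP gives no AESI term list and does not say how an event is flagged as an AESI.

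**The concern.** Spread of toxin effect is the safety question that the protocol singles out for this product class, and the AESI process is its means of answering it. AESI status decides whether the subject is actively questioned about a symptom (protocol 11.6 contrasts this with non-leading general questions). It also decides whether a telephone report leads to a mandatory visit, whether the sponsor hears within 24 hours, and whether the event is counted in the AESI tables. If a sign that the protocol itself associates with toxin spread is not on the list, sites may classify the same event differently, and the AESI tables would not cover the same ground as the warning. AESI frequency is part of the first secondary safety endpoint, so its definition should be fixed and readable from the plan.

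**Working it through.** The documents give no figure to reproduce. The check is a term-by-term comparison, then a separation of what depends on AESI status from what does not.

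**Step 1. Size of the list.** The table in 11.2 has 17 rows of three columns with one empty cell: 17 × 3 − 1 = 50 terms.

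**Step 2. Match each sign in 4.6.2 to the list in 11.2.**

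| Sign in 4.6.2 | Counterpart in 11.2 |
|---|---|
| Asthenia | None; nearest is muscular weakness |
| Generalized muscle weakness | Muscular weakness |
| Diplopia | Diplopia |
| Ptosis | Eyelid ptosis |
| Dysphagia | Dysphagia |
| Dysphonia | Dysphonia |
| Dysarthria | Dysarthria |
| Urinary incontinence | None; nearest are urinary retention and pelvic floor muscle weakness |
| Breathing difficulties | Dyspnea, plus respiratory arrest, depression and failure |

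Matched: 7. Unmatched: 9 − 7 = 2.

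**Step 3. Do the nearest terms close the gap?** Section 4.6.2 names asthenia and generalized muscle weakness as separate signs, so one listed term does not plainly cover both. Urinary retention is the opposite symptom to incontinence. Pelvic floor muscle weakness is a possible mechanism for incontinence, not the symptom a subject would report. The list is also finely divided (palsies, paresis and paralysis of the cranial nerves are separate entries), which invites term-by-term reading. The gap is clearer for urinary incontinence than for asthenia.

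**Step 4. What depends on AESI status for a non-serious case.**

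- Mandatory call-back visit after a telephone contact (9.3.1 and Table 9-1). Telephone visits are at weeks 2 and 8 of the open-label cycles only.
- 24-hour report (11.6.1).
- Entry in the AESI tables (protocol 12.4.2, SAP 8.7.2).

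**Step 5. What does not depend on it.**

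- Recording as an adverse event (11.1) and display in the TEAE tables by system organ class and preferred term.
- Evaluation by the investigator, which 11.6 requires for any subject with an adverse event.
- Scheduled full physical examinations, which include muscle weakness (11.11). Table 9-1 places them at baseline and weeks 1, 2 and 4 of cycle 1, at weeks 1 and 4 of each open-label cycle, and at End of Study.
- 24-hour reporting of any case that is serious.

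**The case against.** The strongest reply is that the list may not be closed. Its lead-in can be read as giving examples, and the questioning follows an AESI Manual that may well name both symptoms. This stands, and it is why the consequence can only be stated as possible. It does not remove the point. The examination trigger in 11.2 refers to the terms printed there. If the list is open, the plan gives about 18 sites no rule for deciding what belongs. If the manual does contain the terms, it differs from 11.2 and still needs reconciling.

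A second reply is that 4.6.2 mentions warning signs alongside AESIs and never says the two sets are the same. That is fair: a subject warning can be wider than a surveillance list. But the documents give no reason for leaving out these two signs while including counterparts of the other seven.

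A reader might infer that the two symptoms would go unexamined. The documents do not support that. The footnote in protocol 2.1 extends the focused examination to symptoms related to AESIs, the investigator evaluates every subject with an adverse event, and full examinations recur on schedule. In the placebo-controlled cycle, weeks 2 and 8 are clinic visits. What is left is narrow. Table 9-1 lists no full examination at the open-label re-treatment evaluation visits (12 and 17). After a week 8 call in cycle 2 or 3, the next scheduled full examination therefore follows the next injection or falls at End of Study.

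**Conclusion.** The mismatch is real: two of the nine signs in 4.6.2 have no counterpart among the 50 terms in 11.2. Non-serious cases of urinary incontinence or asthenia may therefore miss the call-back visit after an open-label telephone contact, the 24-hour AESI report and the AESI tables. This rests on four conditions: sites apply 11.2 term by term, the AESI Manual does not cover the symptoms, the case is not serious, and no listed term is recorded for the same event.

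Two stronger conclusions are not supported. A reader might say that the AESI rate will be too low, but that presumes the two signs belong in the definition, which the documents leave unsettled. A reader might also want a count of missed subjects. The documents give no rate for either symptom, and the Korean safety data in protocol Table 4-4 (265 events) list neither. An assumed 0.5% to 2% of 700 subjects would give 0.005 × 700 = 3.5 to 0.02 × 700 = 14, but neither rate has a source in the documents, and the sum supposes that none of those subjects has a listed term recorded. The size that can be stated is two signs of nine. The events themselves would remain visible in the TEAE tables.

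**What to change.** Reconcile protocol 4.6.2, protocol 11.2 and the AESI Manual to a single term list that includes urinary incontinence and asthenia, or state why either is excluded. Say whether the list is closed. Name that same list in SAP 8.7.2 as the basis for flagging AESIs, so that site classification, 24-hour reporting and the tables use one definition. In the same edit, correct the pointer in 4.6.2, which sends the reader to section 11.1 for AESIs when the list is in 11.2.

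The cost is two terms, one cross-reference and a sentence in the SAP. In conduct it means a few more AESI reports, with the visits and examinations that go with them, and a slightly higher reported AESI rate. No treatment rule or visit schedule changes.

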5. STUDY PURPOSE AND OBJECTIVES

5.1 Study Purpose

The purpose of the study is to assess the efficacy and safety of BoNT/A-DP in the treatment of glabellar lines in comparison with placebo, including efficacy after repeat treatments and long term safety.

5.2 Primary Objective

To assess the efficacy of BoNT/A-DP in reducing the severity of glabellar frown lines following treatment (compared with placebo) based on investigator and subject assessment.

5.3 Secondary Objectives

1. To assess the proportion of responders at maximum frown and at rest at various time points after each treatment, based on investigator and subject assessments.
2. To assess onset of effect and the duration of effect (at maximum frown) after a single treatment with BoNT/A-DP compared with placebo (first treatment cycle), based on investigator and subject assessments.
3. To provide long term safety data of BoNT/A-DP based on multiple treatment cycles and to establish a sufficient safety database to support regulatory approval.
4. To assess the psychological impact of BoNT/A-DP treatment on subjects (in terms of emotional and social functioning and concerns relating to their glabellar lines) in comparison with placebo after a single treatment.
5. To assess subject perceptions of effect of, and satisfaction with, treatment in comparison with placebo (first treatment cycle) and during the open-label extension phase.

6. STUDY DESIGN

6.1 Brief Summary

This multicenter Phase 3 study is comprised of two parts. The first part of the study is a randomized, double blind, placebo-controlled, phase which aims to demonstrate efficacy and safety of BoNT/A-DP compared with placebo. The second part is an open label extension phase to evaluate efficacy after repeat treatments and long term safety.

Subjects can receive a maximum of four treatment cycles over the duration of the study, a single treatment in the first cycle compared with placebo, and up to three subsequent treatments in the open label extension study.

Based on historical data with similar products, it is anticipated that there will be a significant difference in responder rates between BoNT/A-DP and placebo in the first treatment cycle^{11,40,41} and it is anticipated that the duration of effect in subjects administered the active treatment will last approximately 12 weeks³⁶.

6.2 Overall Study Design

The study is a parallel-group, randomized, double blind, placebo-controlled study followed by an open label extension.

6.3 Population to be Studied

A total of approximately 700 subjects of either gender, between 18 and 75 years of age inclusive, who meet all the inclusion criteria and do not meet any exclusion criteria and who provide written informed consent, will be enrolled in the study.

